Date: November 27, 2023

Title: Clinical trial in skin conditions of the foot using a cream enriched with *Melaleuca alternifolia* essential oil.

Description of document: Materials and Methods (Study Protocol: description of the clinical study, including objective and design. Statistical Analysis Plan (description of the statistical considerations for analyzing the data collected in the study) results of the study (Results obtained in the study) and Supplementary data (Annexes).

1. Material and method

Type of study, permits, and inclusion criteria

A randomized, double-blind, multicenter clinical trial was designed, developed at the facilities of the University Center of Plasencia (University of Extremadura, Spain) and at the Escola Superior de Saúde [name] (Polytechnic Institute of Castelo Branco, Portugal), from March to May 2023.

The trial was authorized by the Bioethics Committee of the University of Extremadura (Register No.: 55/2017, Annex 1) and was conducted in accordance with the ethical principles established in the Declaration of Helsinki in accordance with current legislation on biomedical research (Law 14/2007, of 3 June). In addition, all participants joined voluntarily, after signing the informed consent.

The inclusion criteria established were that the participants were free of cosmetic and pharmacological substances in their feet and nails, that they did not have any type of diagnosed allergy to the components of the cream or to the EO of choice and that they maintained correct foot hygiene. Participants who had a condition that compromised their health and had repercussions on the foot or who were under medical treatment incompatible with their participation in the trial were excluded from the study.

Sample

The initial number of participants was 65, of which 9 were excluded because they did not meet the inclusion criteria or because they did not sign the informed consent form (Figure 1). Of the remaining 56 participants, 7 were excluded due to lack of adherence, as they did not attend the review, so the final number of participants was 49 (Figure 1).

[figure not shown]

Figure 1. Flowchart according to CONSORT standards of the process of inclusion of participants in the study.

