The sample consisted of 36 women and 13 men, divided into two age groups: young people between 18 and 30 years old ($22,438 \pm 3,898$) and adults between 31 and 64 years old ($50,212 \pm 9,633$). In terms of origin, 23 were residents of Plasencia (Spain) and 26 in Castelo Branco (Portugal). The descriptive characteristics of the sample are detailed in Table 1.

Table 1. Descriptive characteristics of the sample.

VARIABLES	Total n=49	Origin	Young Men (mean±SD)	Adult Men (mean±SD)	Young Women (mean±SD)	Adult women (mean±SD)
AGE (years)	41,143± 15,485	Spain Portugal	20±2,828 26±NP	46,333±13.317 46,857±10,495	24,111±3,723 19±2	49±9,367 53.50±8.609
	70,545± 12,705	Spain Portugal	80±14,142 69±NP	87,333±17,926 80,714±11,572	68,667±13,684 66,750±8,995	64,411±7,193 66.857±11.016
HEIGHT (m)	1,664±0 ,085	Spain Portugal	1.82±0.113 1.7±NP	1.733±0.025 1.757±0.060	1,652±0.074 1.657±0.049	1.618±0.068 1,616±0.057
	25,404± 3,626	Spain Portugal	24,026±1,280 23,875±np	29,170±6,725 26,148±3,488	25,069±4,334 24,372±3,837	24,611±2,350 25,552±3,548

n: sample size; SD, standard deviation; NP: Not applicable; kg: kilogram; M: Metro; BMI, body mass index; m^2 : Square meter.

Randomization, masking, and experimental design

Participants were randomly assigned to distinct groups using free software Epidat 4.0 (2011, Galicia, Spain). The blinding was double-blind, so that neither the investigators nor the participants knew the group assigned to the participant until the completion of the study and statistical analysis.

The total number of participants was divided into three groups: a control group (T0) (n=12), in which no participants had a skin infection, and two different treatment groups (T1 and T2) (n=37), with diverse levels of EC. The rest of the participants were included in these two treatment groups, including both infected (n=32) and healthy (n=5) participants. Thus, group T1 (n=25) had 23 participants with infection and 2 healthy participants, and group T2 (n=12) had 9 participants with infection and 3 healthy participants.

The clinical evaluation of the participants was carried out before the start of treatment and, subsequently, on days 15, 30, 45 and 60 of treatment, except for cultures, both mycological and bacterial, which were performed at baseline, at 30 days and at 60 days of treatment. All reviews, sampling, and data collected were performed by the same observer.

Choice of EO, base cream, and preparation of treatments

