Scans and measurements were performed in a temperature-controlled room (20-24°C) and participants aired their bare feet for 10 minutes before starting the procedures, to normalize the temperature. In the first session they were weighed and measured (SECA 701, Vogel & Halke Hamburg, Germany), calculating the BMI(2). After normalizing the temperature, the physical examination was carried out, samples were taken, and data were obtained.

The Corneometer CM 825® (Electronic Courage-Khazaka, Cologne, Germany) with a measuring surface of 49 mm, a frequency of 0.9–1.2 MHz and an accuracy of $\pm 3\%$, was used to assess the superficial hydration of the skin (3). Five reference points were measured, both at the dorsal level and at the plantar level (Figure 2), obtaining three measurements from each point to later calculate the average hydration of each location analyzed.

[figure not shown]

Figure 2. Location of the 5 reference points on the feet for assessment of superficial hydration. (A) Dorsum of the foot: (1) dorso-distal point, above the central metatarsal heads. (B) Sole of the foot: (2) interdigital-plantar point, between 3rd and 4th digital space, (3) central point of the internal arch, (4) central point of the external arch, and (5) central point of the calcaneus.

Regarding the diagnosis of possible infections present in the feet, the following tests were performed:

- Wood's Light Examination

The feet of the participants were examined with a Wood L1004® lamp (Weelco, Barcelona, Spain) at maximum power (41) and at a distance of 10-15 cm from the surface to be examined. Long-wave ultraviolet radiation allows visual observation of the fluorescence emitted by *Pseudomonas aeruginosa*, *Microsporum audouinii*, *Microsporum canis*, *C. minutissimum*, *T. schoenleinii*,(4) among

others, whose color varies depending on the pathogen. The areas that fluoresced were recorded along with the color of the fluorescence in each review conducted from the beginning of the study to the day of its completion.

- Potassium hydroxide (KOH) test and mycological culture

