Statistical analysis was performed using the statistical analysis program IBM-SPSS Statistics for Windows version 25 (IBM Corp. Armonk, NY, USA). Some figures have been obtained using the Python programming language, using the Seaborn library (Waskom, M. L., (2021). Seaborn: statistical data visualization. *Journal of Open-Source Software*, 6(60), 3021, <https://doi.org/10.21105/joss.03021>).

Normality was assessed using the Shapiro-Wilk test. To evaluate the influence of different variables on infection remission, a Cox regression model was used, and survival curves of significant factors were plotted. To compare the efficacy of different EC concentrations, survival curves were compared using the Log-rank test. The Mann-Whitney U test was used to assess hydration averages according to sex. To check if there were improvements in hydration due to the use of the cream with different concentrations of EC (T1 and T2) compared to the control group (T0), hydration levels were compared using Kruskal-Wallis tests, using the Mann-Whitney U test with correction of p-values by the Bonferroni method for multiple comparisons.

In all statistical tests, significance was considered when p-value<0.05 and high significance when p-value<0.01.

2. Results

Analysis of the Elemental Composition of Commercial S. S.

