Of the participants who developed skin infections, 23 were women and 9 were men. The prevalence of skin infections by sex is shown in Table 3.

Table 3. Prevalence of infections as a function of sex.

Sex	Infections			Total
	Fungal	Bacterial	Mixed	
Women	3 (9.3%)	13 (40.6%)	7 (21.8%)	23 (71.7%)
Men	1 (3.1%)	6 (18.8%)	2 (6.4%)	9 (28.3%)
Total	4 (12.4%)	19 (59.4%)	9 (28.2%)	32 (100%)

%: Percentage.

The colorations observed with Wood's light in the interdigital spaces were coral red and opaque blue (Figure 3). The coral-red coloration corresponds to a superficial bacterial infection of the skin caused by *C. minutissimum*, known as erythrasma, and the dull blue coloration corresponds to a fungal infection caused by the dermatophyte *Trichophyton schoenleinii*.

[figure not shown]

Figure 3. Fluorescence of different color emitted by pathogens under Wood's light in interdigital spaces of the feet. (A and B) erythrasma with coral-red coloration (*) and (B) suspected *Trichophyton schoenleinii* with bluish coloration (↑).

Mycological cultures were used to determine the causative agents of fungal infections. The dermatophytes and yeasts that were identified were: *Trichophyton schoenleinii*, *Trichophyton verrucosum*, *Trichophyton tonsurans* and *Candida albicans*. On the other hand, the following bacteria were identified in bacterial cultures: *Corinebacterium minutissimum*, *staphylococcus haemolyticus*, *staphylococcus epidermidis*, *staphylococcus lugdunensis*, *micrococcus luteus* and *micrococcus sp.*

Efficacy of treatments

To test whether the EC-enriched cream was effective against fungal infections, the cumulative survival curves of the two treatments, T1 and T2, were plotted (Figure 4). 100% of fungal infections resolved within 30 days with both treatments, although the EC curve at 1% was higher than 0.5%.

[figure not shown]

Figure 4. Cumulative survival curves as a function of the two treatments for fungal infections.

In fact, the mean time to achieve remission in the T1 group (1%) was 11.61 days, compared to 14.00 days in the T2 group (Table 4). However, according to the Log-rank test, the differences between the two groups were not statistically significant (p -value=0.611). Therefore, both concentrations have similar efficacy in terms of the time required to achieve remission of infection.

Table 4. Mean and median survival time (in days) of remission of fungal infection for the two EC concentrations.

Group	Media				Median			

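### Remission is undefined and every follow-up culture is on treatment, so the claim that all fungal infections resolved within 30 days lacks a day-60 status and shows no more than on-treatment negativity

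*Combined protocol and SAP*

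**What the plan says.** **Schedule.** Under *Randomization, masking, and experimental design*, clinical reviews take place "on days 15, 30, 45 and 60 of treatment". Cultures, mycological and bacterial, are the exception, "which were performed at baseline, at 30 days and at 60 days of treatment". No visit or sample after treatment is described.

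**Other follow-up test.** Under *Exploration, sampling, and diagnostic tests*, the Wood's light paragraph says: "The areas that fluoresced were recorded along with the color of the fluorescence in each review conducted". No recurrence result from it is reported.

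**Definitions.** The same section classes a participant as infected when both tests of the relevant pair are positive (KOH and culture for fungi, Gram stain and culture for bacteria). Remission, confirmation of remission and relapse are not defined anywhere.

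**Analysis.** Under *Variables and statistical analysis*: "To evaluate the influence of different variables on infection remission, a Cox regression model was used", and "To compare the efficacy of different EC concentrations, survival curves were compared using the Log-rank test". No rule for sustained remission or recurrent events is given.

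**Result.** Under *Efficacy of treatments*: "100% of fungal infections resolved within 30 days with both treatments". Table 4 gives mean times to fungal remission of 11.61 days (1%) and 14.00 days (0.5%), with no median in either arm. Table 5 gives bacterial means of 49.35 and 44.82 days, with a median of 60.0 days for 0.5% only. The comparison by sex speaks of healing time and faster resolution.

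**The concern.** A negative sample from skin that is still receiving an antimicrobial cream can mean three things: the organism is gone, it is temporarily suppressed, or the sample missed it. The day-60 culture could help with the third possibility and would also detect relapse under treatment. However, a time-to-event analysis with one event per participant, and no stated requirement that the event persist, has no place for a positive result that follows a negative one.

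The fungal result shows this most clearly. If everyone has had the event by day 30, the day-60 fungal cultures have no evident role in the reported result, and their findings are not shown.

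What is at stake is the meaning of the efficacy claim. If some day-30 negatives turned positive again, the remission proportion is too high and the time to remission too short. If none did, the report would be stronger for saying so. In either case, terms such as resolved and healing suggest an outcome that was not observed off treatment.

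**Working it through.** **1. Reproducing the stated figures.** No remission counts by arm and visit are given, so the 100% cannot be rebuilt. The confidence intervals for the means can be checked as estimate ± 1.96 × SE:

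| | Mean (SE) | Recomputed | Stated |
|---|---|---|---|
| Fungal 1% | 11.61 (2.68) | 6.36 to 16.86 | 6.36 to 16.86 |
| Fungal 0.5% | 14.00 (4.04) | 6.08 to 21.92 | 6.09 to 21.91 |
| Bacterial 1% | 49.35 (2.38) | 44.69 to 54.01 | 44.68 to 54.01 |
| Bacterial 0.5% | 44.82 (4.38) | 36.24 to 53.40 | 36.2 to 53.40 |

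They agree to rounding, so Tables 4 and 5 are internally consistent.

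**2. Do the fungal means fit the schedule?** If remission is dated at a follow-up culture, the earliest date is day 30 and no mean can be below 30. If it is dated at any scheduled review, the earliest is day 15 and no mean can be below 15. The stated means are 11.61 and 14.00. Allowing entries at time 0, with all events at 0, 15 or 30 and no censoring, the mean is 15k/n for whole numbers k and n. The smallest n giving 11.61 to two decimals is 31 (15 × 24/31 = 11.613), but T1 has 25 participants. The smallest n giving 14.00 is 15 (15 × 14/15), but T2 has 12. Remission was therefore dated, or the units counted, in some way that the document does not describe.

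**3. Does Table 4 fit 100% resolved?** If every participant has the event, the survival curve falls to zero and a median exists. Table 4 reports none. For bacterial infection, the text reads a missing median as meaning that fewer than half resolved.

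**4. How many fungal infections?** *Test results for microbiological diagnostics* gives 4 fungal + 9 mixed = 13. Table 6 gives 8. The bacterial counts also differ: 19 + 9 = 28 against 20 in Table 6.

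**5. What could the day-60 cultures show?** Exact (Clopper-Pearson) 95% intervals for the proportion still negative at day 60, taking all as negative at day 30. With no reversions the lower limit is 0.025^(1/n): 0.025^(1/13) = 0.753 and 0.025^(1/8) = 0.631.

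| Reversions (assumed) | n = 13 | n = 8 |
|---|---|---|
| 0 | 100% (75.3-100) | 100% (63.1-100) |
| 1 | 92.3% (64.0-99.8) | 87.5% (47.3-99.7) |
| 2 | 84.6% (54.6-98.1) | 75.0% (34.9-96.8) |

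The reversion counts are illustrative; none is reported. Even with none, the upper limit for the reversion rate is 24.7% (n = 13) or 36.9% (n = 8).

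**6. Illustration of sampling error.** Suppose one sample misses a fraction f = 0.10 to 0.30 of persisting infections; this range is assumed and has no source in the document. One negative then misclassifies 10-30% of persisting infections. Two independent negatives misclassify f² = 1-9%. Independence is optimistic for the same foot under the same cream, so the real gain would be smaller.

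**7. Bacterial infection.** A Kaplan-Meier median is an event time, so a T2 median of 60.0 days means that at least one T2 remission was dated at day 60, the last sample, and cannot be confirmed. The text also reads this median as half of T2 being in remission at study end, which holds only if nobody reverted.

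**8. Room for off-treatment follow-up.** The trial ran "from March to May 2023". Taking 1 March to 31 May gives 91 days, and 91 − 60 = 31 days at most after treatment. Anyone starting on or after 1 April has none.

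**The case against.** The strongest objection is that the document never says the analysis ends at the first negative result. Cox and log-rank methods can be applied to time to sustained remission just as well. A reader might infer that a day-30 negative was fixed as a success and that a day-60 positive changed nothing. The text does not support that as fact: remission is undefined, and the means of 11.61 and 14.00 days do not fit a first negative culture at day 30 among infected participants. Wood's light was recorded at every review and may have contributed. This objection stands. What survives it is that no rule is stated, that the methods as described do not count a later positive, and that the day-60 status is not reported.

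Three further objections also have force:

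- A second on-treatment culture cannot distinguish cure from suppression, because continuing suppression would give two negatives.
- Requiring confirmation leaves first negatives at day 60 in limbo unless a rule is given for them.
- Both comparisons of T1 with T2 are already non-significant (p = 0.611 and 0.130), and nothing shows that a rerun would change this. No infected participant received the base cream alone, so remission cannot be attributed to the oil however it is confirmed.

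These limit what the re-analysis can achieve. They do not justify leaving day-60 results unreported, or describing on-treatment negativity as resolution or healing.

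**Conclusion.** The point holds in a limited form. All follow-up cultures are on treatment, remission has no definition and no requirement to be sustained, and the 100% fungal claim comes without the day-60 status of those it counts. Nothing was measured after treatment.

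The size of any bias is unknown. What can be given is the precision: with no reversions, the data would be compatible with sustained negativity as low as 75.3% (n = 13) or 63.1% (n = 8). Those intervals take the 100% at face value, although the missing medians and the mean times leave it in doubt.

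A reader might go further and conclude that infections did relapse, or that the true figure is nearer 85%. The document reports no reversion. The 85% (11 of 13) and the 10-30% miss rate are purely illustrative.

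The change is worth making because it is cheap and bears directly on the main efficacy statement. The lack of an infected control remains the larger limitation.

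**What to change.** 1. **Define and date remission.** State which tests count, whether one negative is enough, and which date is used. Reconcile this with the means of 11.61 and 14.00 days, the missing medians in Table 4, and the fungal counts of 13 and 8.
2. **Report the day-60 status** of everyone negative at day 30, by arm and infection type, including reversions, with exact confidence intervals.
3. **Add a sensitivity analysis of T1 versus T2** in which a day-30 negative counts as remission only if day 60 is also negative. Show first negatives at day 60 separately as unconfirmed, and run the comparison twice: once counting them as remissions and once not.
4. **Limit the wording.** Replace resolved and healing with culture-negative while on treatment, and state that off-treatment cure was not assessed.

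Items 2 and 3 address sampling error and relapse under treatment; item 4 addresses suppression versus cure.

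**Cost.** Re-analysis and rewording only, with no new visit or sample, provided the day-60 cultures were taken as the text describes. The downside is fewer confirmed remissions and a group of day-60 clearances that stays unconfirmed, which mainly affects the bacterial result.

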After reviewing the available literature, the essential oil (EO) of *M. alternifolia* was chosen for its antibacterial and antifungal characteristics (16–19). There were 3 types of commercial *M. alternifolia* EO from the brands Marnys® (Cartagena, Spain), Naissance® (Neath, United Kingdom) and Esencias Lozano® (Murcia, Spain). However, the choice of the specific commercial EO depended on the results obtained from the analysis of its composition. This analysis was performed using gas chromatography mass spectrometry (CG-MS) and the results obtained were contrasted with those available in the online database SpectraBase (WILEY, John Wiley & Sons).

The cream used as a base for the incorporation of the different concentrations of EO tested was a hand and nail cream (*La Chinata*®, Plasencia, Spain), in which Extra Virgin Olive Oil is used. This cream was chosen after verifying that none of its components were allergens for the skin of the participants according to Regulation 1223/2009(1). In addition, it was the treatment received by patients in the T0 group, in whom no type of EC was added.

To test the possible efficacy of the chosen *M. alternifolia* EO as a treatment against infections, the base cream was enriched with different concentrations of EO. Specifically, 1% for the T1 treatment group

and 0.5% for the T2 treatment group. The emulsion of the EO and the base cream was carried out by means of a magnetic stirrer (Agimatic-N, Barcelona, Spain) under sterile conditions (laminar flow cabinet, Telstar AV-100), adding the necessary volume of EC until the desired two concentrations were achieved.

Treatments were administered to participants in the form of prefilled 15ml syringes under sterile conditions with enough for 15 days of treatment. Along with the treatment, all the necessary information was provided on the hygienic habits to follow (washing the feet properly with soap and water and drying them properly with a towel for exclusive use), the correct way of applying the treatment, the daily volume of treatment for each foot (0.5ml/2 times a day).

Exploration, sampling, and diagnostic tests

Sociodemographic data (age and sex), medical and podiatric history, allergies and pharmacological treatments prescribed, as well as hygiene habits, were obtained through the completion of a Google Forms survey (Annex 2).

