A skin sample was taken following the standard procedure described for the diagnosis of mycosis (5). The epithelial surface was disinfected with 70° alcohol and a sample was collected from the affected area by scalpel scraping. Subsequently, the sample was analyzed using two different procedures. The 30% KOH test (35.3g/100ml distilled water) (Labbox, Barcelona, Spain) followed by conventional light microscopy observation to identify the infective fungal agent, and microbiological culture on Sabouraud dextrose agar with chloramphenicol and cycloheximide (Condalab, Torrejón de Ardoz, Madrid), at a constant temperature (between 25°C and 28°C) for 2 to 4 weeks, in order to inhibit molds and bacteria and observe the growth of the infective fungal agent. Participants with infection were considered to be those who had positive results in both tests, excluding cases in which only one test was positive.

- Bacteriological culture

A skin sample was taken following the standardized procedure for microbiological analysis (6). The skin was disinfected with 70° alcohol and a sample was taken by smear with a sterile swab from the affected surface. Again, the analysis was carried out using two distinct and independent procedures. A Gram stain was performed to identify bacteria and the sample was inoculated with Sabouraud dextrose broth (SDA) (Merck, Germany), at a constant temperature (between 27°C and 31°C) for 1 to 3 days. Participants with infection were considered to be those who had positive results in both tests, excluding cases in which only one test was positive.

Variables and statistical analysis

The following variables were analyzed: sociodemographic (sex and age), anthropometric (weight, height, and BMI), hygiene-related habits (frequency of foot washing, use of flip-flops in showers/pools, type of footwear and socks and frequency of sock change), presence or absence and type of infection, degree of hydration and concentration of EC group T0 (0%), group T1 (1%) and group T2 (0.5%). Of these variables, age, weight, height, BMI, and hydration were considered quantitative compared to the rest that were analyzed as qualitative.

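### In the text available, no skin-reaction or tolerability measure is listed, analysed or reported during treatment, although the authors name allergenic components in the oil

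*Combined protocol and SAP*

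**What the plan says.** **Variables.** Section 1, Variables and statistical analysis, lists sex, age, weight, height, BMI and hygiene habits, followed by "presence or absence and type of infection, degree of hydration and concentration of EC group T0 (0" and the two oil concentrations. The outcome methods that follow are Cox regression and log-rank tests for remission, and rank tests for hydration. Hydration is tested for improvement, that is, as a benefit.

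**Allergy.** Entry required that participants "did not have any type of diagnosed allergy to the components of the cream or to the EO of choice". Of the base cream the document says: "This cream was chosen after verifying that none of its components were allergens for the skin of the participants". The Results, in the part on oil composition, say the oil was chosen partly for a low content of components that can interact with drugs or cause allergy, and name terpinolene, alpha-terpinene and sabinene.

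**Opportunities to observe.** Clinical evaluation took place at baseline and "on days 15, 30, 45 and 60 of treatment". "All reviews, sampling, and data collected were performed by the same observer". Under Wood's light, "The areas that fluoresced were recorded along with the color of the fluorescence in each review". Item 16 of the Annex 2 questionnaire asks about current itching, stinging and burning of the feet. The methods describe that survey as the source of background, history, medication and hygiene data, and do not mention repeating it on treatment.

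**Non-attenders.** Of 56 eligible participants, "7 were excluded due to lack of adherence, as they did not attend the review". The text gives neither their arm nor whether they had used any cream.

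**The concern.** Every allergy safeguard described acts before the first application: the entry criterion, the check of the base cream and the choice of oil. Excluding people with a diagnosed allergy cannot detect irritation or new sensitisation that arises during two months of twice-daily use. The choice of oil did not remove the issue. In Table 2 the selected brand has the lowest terpinolene of the three (3.72%, against 4.26% and 4.65%) but the highest alpha-terpinene (13.58%, against 13.10% and 11.23%).

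At stake is what the trial can say to the next user or investigator of the 1% or 0.5% cream. If reactions were not recorded at the visits, no later analysis can recover them. If they were recorded, leaving out the counts means a reader cannot tell none from some.

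**Working it through.** **1. Participant flow (Section 1, Sample, and Randomization, masking, and experimental design).** The document's own numbers reproduce:

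- 65 − 9 = 56 and 56 − 7 = 49 analysed.
- By group, 12 + 25 + 12 = 49.
- Oil groups: 25 + 12 = 37. Infected 23 + 9 = 32, not infected 2 + 3 = 5, and 32 + 5 = 37, which agrees with "including both infected (n=32) and healthy (n=5) participants".
- Not attending the review: 7/56 = 12.5%.

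**2. Where a tolerability item could appear.**

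| Place | Content found | On-treatment reaction item? |
|---|---|---|
| Analysed variables | demographics, anthropometry, hygiene, infection, hydration, concentration | none |
| Statistical tests | remission, hydration | none |
| Results, text and Tables 2 to 12 | oil composition, microbiology, remission, hygiene, Cox models, hydration | none, and no statement that none occurred |
| Annex 2, item 16 | symptoms on the day of the survey | repeat use not described; not analysed |
| Figure 1 and the annex text before questionnaire item 15 | not available | unknown |

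**3. Scale of what the data could have shown.** No reaction count is given, so these figures are hypothetical and describe only the size of the groups.

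One-sided 95% upper limit if zero reactions had been recorded among n participants: 1 − 0.05^(1/n).

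- Both oil groups, n = 37: 7.8%
- T1, n = 25: 11.3%
- T2, n = 12: 22.1%

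Chance of seeing at least one reaction at a true rate p: 1 − (1 − p)^n. The document gives no rate, so p is assumed over a range.

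| Assumed p | T1 (25) | T2 (12) | Both (37) |
|---|---|---|---|
| 1% | 22% | 11% | 31% |
| 2% | 40% | 22% | 53% |
| 5% | 72% | 46% | 85% |

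Groups of this size can describe common reactions but cannot exclude uncommon ones or rank the two concentrations.

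**The case against.** **The gap may be one of reporting only.** The methods lists are not exhaustive: Wood's light findings were recorded and reported but are not named among the variables, and the chi-square tests in Table 7 are not in the statistical methods. Absence from the list is therefore weak evidence that nothing was noted at visits. This stands. A reader might infer that reactions were never looked for; the text shows only that none are listed, analysed or reported.

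**The seven non-attenders.** A reader might infer that some left because the cream irritated them, and could build a worst case: all seven on oil, all dosed, all reacting, and none among the 37, giving 7/(37 + 7) = 15.9%. Nothing in the documents supports any of those steps. The text says they did not attend the review and puts this down to poor adherence; it does not show that any of them applied the cream. Figure 1 is the natural place for their arm and reason, and it was not available. The figure is a bound on ignorance, not an estimate.

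**The product as an allergen.** It is tempting to say that the authors regard the cream as a possible allergen. They say this of certain oil components, not of the finished 0.5% or 1% cream, and they report that the base cream was checked.

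**Limited yield.** The document makes no tolerability claim, the groups are small, and itching, stinging and burning are also symptoms of infection. T0 contained no infected participants, so an observer who knows that a participant is infected also knows the cream contains oil. These points limit what the data could show. They do not remove the expectation that a randomised trial of a treatment reports harms by arm.

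**Conclusion.** The concern holds as a gap in safety information. In the text available, no on-treatment skin reaction or tolerability measure is listed, analysed or reported for the 37 analysed participants in the oil groups, while the document itself names allergenic components of the oil. Hydration does not fill the gap, because it is analysed as a benefit.

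No efficacy or hydration result is affected, and the finding does not suggest that the cream was poorly tolerated. It supports only this: the document gives no basis for a tolerability statement about either concentration, in either direction. The conclusion assumes that Figure 1 and the missing annex text contain no reaction data; if they do, the point narrows to moving those data into the Results. It should be acted on, because the information is basic and cheap to collect.

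**What to change.** **For this completed trial.** Report by group, with exact intervals, any reaction counts that exist. Give the arm and reason for the seven who did not attend the review, if Figure 1 does not already do so. If no reaction data exist, state that tolerability was not assessed.

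**For a repeat or extension.**

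1. At the existing reviews on days 15, 30, 45 and 60, re-ask Annex 2 item 16, and have the same observer record any visible skin reaction (present or absent, site, simple grade) during the foot examination.
2. Tabulate new or worse findings against the participant's own baseline, by arm and baseline infection status, with visible reactions in a separate column. Treat the table as descriptive.
3. For anyone who misses a review, record arm, whether any cream was used, and the reason. Keep everyone who used cream in the tolerability denominator.

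**Cost.** One existing question and one observer item at four existing visits, a few minutes each, plus one call per non-attender (seven here). The main drawback is overlap with infection symptoms: relief of infection and irritation from the oil could cancel out in item 16, which is why the observer item is kept separate. Comparison among uninfected participants would be thin here, with 12 in T0, 2 in T1 and 3 in T2, and the result could not by itself choose between 1% and 0.5%.
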